7. EFFICACY ANALYSES

7.1. General Considerations

Unless otherwise specified, efficacy analyses will be conducted using the mITT population according to the randomized treatment assignment and will be stratified by the randomization stratification factors (geographic region, presence of metastatic disease, and baseline age). If the group of patients from any of the individual randomization stratification factors (eg, with presence of metastatic disease) comprises < 10% of the entire mITT population, this stratification factor will be collapsed for stratified analyses. In addition, if there were < 15 patients in one of the 12 strata, stratification factors of presence of metastatic disease and baseline age would be used in the stratified analysis for more robust strata-adjusted estimation of treatment effect. If there is a discrepancy > 5% between interactive web response systems (IWRS) and CRF on a stratification factor, the stratification factor reported in CRF will be used as primary analyses and that reported in IWRS will be used as sensitivity analyses, unless otherwise specified. In the case of a discrepancy > 5% between IWRS and CRF on the presence of metastatic disease stratification factor, patients with metastatic prostate cancer will be identified from CRF instead of from IWRS.

For efficacy endpoints related to testosterone test results, analytical testosterone results from the central bioanalytical laboratory using a liquid chromatography–tandem mass spectrometry method, with a lower limit of quantification of 5 ng/dL, will be used. Unless the endpoints are related to testosterone recovery, results from safety follow-up, 60-day and 90-day testosterone recovery (refer to [Table 2](#)) will be excluded from the efficacy analyses.

7.2. Multiplicity Adjustment

The primary and the key secondary efficacy analyses will be performed at an overall two-sided type I error of 0.05. A test will be deemed statistically significant if the two-sided p-value rounded to 4 decimal places is less than 0.05. If the result of the primary endpoint analysis meets the respective evaluation criterion of the primary endpoint, the key secondary endpoints will then be tested with a fixed-sequence testing procedure (as illustrated in [Figure 2](#)) to maintain the overall familywise error rate of 0.05 for the testing of primary and key secondary endpoints.

The key secondary endpoints with alpha protection for labelling purposes are identified and defined in [Section 7.4.1](#).

All p-values (if provided) aside from the endpoints listed in the testing order are not adjusted in multiplicity, thus are at a nominal level of 0.05.

7.3. Primary Efficacy Endpoint

The study has two separate evaluation criteria for the primary efficacy endpoint to support different regulatory requirements for assessing benefit:

- Evaluation Criterion 1: to determine whether the sustained castration rate for relugolix is $\geq 90\%$. The lower bound of the 95% CI for the cumulative probability of sustained testosterone suppression in the relugolix treatment group will be calculated and must be at least 90% for this criterion to be met.

- Evaluation Criterion 2: to establish the noninferiority of relugolix to leuprolide acetate 3-M depot injection, as assessed by the cumulative probability of sustained testosterone suppression. The lower bound of the 95% CI for the difference in the cumulative probability of sustained testosterone suppression between the 2 treatment groups will be calculated and must be greater than or equal to the noninferiority margin of –10% for this criterion to be met.

Evaluation Criterion 1 is a regulatory requirement from the United States Food and Drug Administration (FDA). Evaluation Criterion 2 is required by European Medicines Agency (EMA) and Japanese Pharmaceutical and Medical Device Agency (PMDA). For the FDA, Evaluation Criterion 1 is the trial success criterion for the primary efficacy endpoint, while Evaluation Criterion 2 is the first to be tested in the order of ranked key secondary endpoints to assess noninferiority of relugolix compared with leuprolide acetate after Evaluation Criterion 1 is met.

7.3.1. Primary Efficacy Analyses

The primary hypotheses associated with two evaluation criteria for the primary endpoint in this study are:

1. Hypothesis 1, corresponding to Evaluation Criterion 1: the cumulative probability of testosterone suppression to < 50 ng/dL (1.7 nmol/L) for relugolix while on study treatment from Week 5 Day 1 through Week 49 Day 1 is $\geq 90\%$.

Null hypothesis H_{01} : $\pi_R < 0.9$ versus Alternative hypothesis H_{a1} : $\pi_R \geq 0.9$

2. Hypothesis 2, corresponding to Evaluation Criterion 2: relugolix is noninferior to leuprolide acetate 3-M depot injection, as assessed by the cumulative probability of sustained testosterone suppression with a noninferiority margin of –10%.

Null hypothesis H_{02} : $\pi_R - \pi_L < -10\%$ versus Alternative hypothesis H_{a2} : $\pi_R - \pi_L \geq -10\%$

where π_R and π_L are the sustained castration rates for the relugolix and leuprolide acetate groups, respectively.

The primary analysis is the calculation of the Kaplan-Meier cumulative estimate of the proportion of patients who achieve and maintain castrate levels of testosterone (< 50 ng/dL) from Week 5 Day 1 through Week 49 Day 1.

The 95% CI for the Kaplan-Meier estimation is calculated using the exponential Greenwood formula via log-log transformation of the survival function.

Variance of treatment difference will be calculated using the formula

$$\hat{V}[\widehat{S}_R(t) - \widehat{S}_L(t)] = \hat{V}[\widehat{S}_R(t)] + \hat{V}[\widehat{S}_L(t)];$$

Where each of the variance of the Kaplan-Meier estimate will be calculated using the Greenwood's formula

$$\hat{V}[\hat{S}(t)] = \hat{S}(t)^2 \sum_{t_i \leq t} \frac{d_i}{n_i(n_i - d_i)}$$

where n_i denotes the number of patients at risk at time t_i and d_i denotes the number of events observed at time t_i . 95% CI of treatment difference will be calculated via linear transformation of the difference in survival function with pooled variance, as follows:

$$[(\widehat{S}_R(t) - \widehat{S}_L(t)) - 1.96 \sqrt{\widehat{V}[\widehat{S}_R(t) - \widehat{S}_L(t)]}, (\widehat{S}_R(t) - \widehat{S}_L(t)) + 1.96 \sqrt{\widehat{V}[\widehat{S}_R(t) - \widehat{S}_L(t)]}].$$

Survival functions, starting at the Week 5 Day 1 (Day 29) to Week 49 Day 1 (Day 337), will be plotted and summarized by treatment group.

7.3.1.1. Definition of Testosterone Test Result at Week 5 Day 1

Serum concentration of testosterone at Week 5 Day 1 can be obtained at targeted Study Day 29, with a visit window from Day 22 to Day 43 inclusive (see [Table 2](#)). If more than one test result lies within the visit window, the result with the study day closest to Day 29 target date will be used. If there are two results equidistant to the scheduled target study day, the earlier assessment will be used as testosterone test result at Week 5 Day 1.

7.3.1.2. Kaplan-Meier Analysis and Censoring Rules

In general, patients with testosterone escape (any testosterone test result rising above the castration level [≥ 50 ng/dL]) from Week 5 Day 1 through Week 49 Day 1 will be considered as an event in the Kaplan-Meier analysis. The time from the date of the first dose to date of the first testosterone escape will be considered as the event time.

Patients who have not reached castration level at Week 5 Day 1 will be considered as having had an event at the target day of Week 5 Day 1.

Patients who discontinued from the study prior to Week 5 Day 1 will be censored at the target day of Week 5 Day 1. In addition, patients without a Week 5 Day 1 assessment will be considered to have had an event at the target day of Week 5 Day 1.

For patients reaching castrate levels at Week 5 Day 1, the following rules will be applied to the Kaplan-Meier analysis for estimation of sustained castration rate with consideration for missed visits. Time to event or censoring, whichever occurs first, will be used in Kaplan-Meier analysis.

- a) Patients who had one or more consecutive missed visits (ie, a visit gap of > 42 days) and had a non-castrate assessment immediately after the missed visit(s) will be considered as having an escape at the target day of the earliest missed visit prior to the non-castrate assessment;
- b) Patients with one missed visit who has a castrate assessment immediately before and after the missed visit will be assumed to be castrated at the missed visit;
- c) Patients with two or more consecutive missed visits (ie, a visit gap of > 70 days) and who had a castrate assessment immediately before and after the missed visits will be censored at the last available testosterone assessment prior to the missed visits.

Note: A visit gap of 70 days for two missed visits was used to consider the duration between two expected visits (8 weeks), plus the visit windows allowed per protocol (7 days for each

expected visit with a total of 2 weeks as visit window for two visits). A visit gap of 42 days for one missed visit was used to consider the visit of every 4 weeks, and ± 7 days as the visit window, per protocol.

Otherwise, patients will be censored at the last available assessment prior to the follow-up visits, including patients who discontinue from the trial for reasons other than a non-castrate testosterone level.

If the above censoring rules are applied to a patient in multiple instances, the date of the earliest censoring for missed visits will be used as the date of censoring.

In addition, patients who had initiated therapies known to suppress testosterone (refer to [Appendix Table 1](#)) will be censored at the time of last testosterone assessment prior to the initiation of such therapies.

The time to event or censoring, whichever comes first, will be summarized by the Kaplan-Meier method. If the event time or censoring time is after Day 337, Day 337 will be used as the event time or censoring time.

For Hypothesis 1:

Estimation of the cumulative probability of testosterone suppression to < 50 ng/dL at Week 49 Day 1 (Day 337) for relugolix arm will be presented along with the 95% CI.

Similarly, estimation of the cumulative probability of testosterone suppression to < 50 ng/dL at Week 49 Day 1 (Day 337) for leuprolide acetate will be presented along with the 95% CI.

For Hypothesis 2:

Treatment difference in the cumulative probability of testosterone suppression to < 50 ng/dL at Week 49 Day 1 (Day 337) between relugolix and leuprolide acetate arms will be presented along with the 95% CI.

7.3.2. Sensitivity Analyses

To assess the robustness of the primary analyses for Evaluation Criteria 1 and 2, the following sensitivity analyses of the primary endpoint will be performed.

7.3.2.1. Sensitivity Analysis 1

Analyses of the primary endpoint will be repeated in the per-protocol population.

7.3.2.2. Sensitivity Analysis 2

In addition to the censoring rules under Section [7.3.1.2](#), patients who had received concomitant medications and herbal supplements that could possibly affect testosterone level during study treatment will be excluded from the analysis.

7.3.2.3. Sensitivity Analysis 3

Patients who had missed two or more consecutive visits after Week 5 Day 1 (censoring rule c in Section 7.3.1.2) or discontinued from the study early will be considered to have an event at the target day of the earliest missed visit.

7.3.2.4. Sensitivity Analysis 4

In order to assess the impact of delayed testosterone suppression to castration level, analyses of the primary endpoint will be repeated by considering that patients who have not reached castration level at Week 5 Day 1 are censored at Week 5 Day 1.

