2.2. Sample Size Justification

The following assumptions were used to determine the sample size for this study:

- True probabilities of sustained testosterone suppression are 94% and 96% for relugolix and leuprolide acetate, respectively;
- 2:1 randomization ratio (relugolix: leuprolide acetate);
- Dropout rate: 15%.

For Evaluation Criterion 1, 610 patients in the relugolix group will provide approximately 90% power to rule out a fixed probability of sustained testosterone suppression of < 90% at a two-sided type I error rate of 0.05.

For Evaluation Criterion 2, with a noninferiority margin of -10% and an overall two-sided type I error rate of 0.05, a total of approximately 915 patients (610 receiving relugolix, 305 receiving leuprolide acetate) will yield at least 99% power to declare the noninferiority of relugolix to leuprolide acetate. The 10% noninferiority margin for the comparison of relugolix versus

leuprorelin is based on regulatory precedence of pivotal assessment of gonadotropin-releasing hormone (GnRH) antagonist degarelix versus leuprorelin as well as studies of branded GnRH agonist generics.

The primary analysis will be performed separately for each evaluation criterion using data collected through 48 weeks after enrollment of approximately 915 patients.

Approximately 915 patients will be randomized in order to fulfill the regulatory requirements of all participating countries included in the primary efficacy endpoint of this study.

Under amendment 3 the study is also powered for the secondary endpoint of castration resistance free survival in the high-risk subgroup of patients with metastatic disease, although this is not part of the primary analysis. Approximately 107 confirmed castration-resistance events (ie, PSA progression while castrated or deaths due to any reasons) will need to be observed (or approximately 390 patients with metastatic disease will need to be enrolled) to detect a hazard ratio of 0.55 (relugolix vs. leuprolide acetate) with 85% power and a two-sided type I error of 5%, assuming a castration-resistant event-free rate of 60% at 48 weeks for the control arm, an 18-month enrollment period, 12 months of additional follow-up, and a 15% dropout rate.

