4.3.3. Treatment Period

The treatment period is defined as the period of time from the date of the first dose of study drug through the date of last dose. The treatment period per protocol is 48 weeks (Treatment Day 336). For patients in the leuprolide acetate treatment arm, treatment period ends 12 weeks after the last leuprolide acetate injection.

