5.6. Prior and Concomitant Medications

Prior and concomitant medications taken during the study treatment period will be summarized for all patients in the mITT population by treatment group. Medications are considered concomitant if medications were used during the study treatment period. Medications will be coded using the World Health Organization (WHO) Drug Dictionary and summarized according to the Anatomical Therapeutic Chemical (ATC) Classification System and generic medication name.

Use of antiandrogens initiated during the first 4 weeks of study treatment (including bicalutamide, flutamide, nilutamide, and enzalutamide) will be summarized separately.

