3.0	06NOV2019	
 1. Aligned with FDA review comments, changed ≤ 50 ng/dL to < 50 ng/dL for castration level and changed ≤ 20 ng/dL to < 20 ng/dL for profound castration level. 2. To address FDA review comments, added “sustained profound castration rate from Week 5 Day 1 through Week 49 Day 1 as a secondary endpoint, in Table 1, Sections 7.4.2 and 7.4.3.2. 3. To address FDA review comments, similar censoring rules for the primary analysis of sustained castration rate applied to sustained profound castration rates in Section 7.4.3.2.

APPENDIX 1: LIST OF MEDICATIONS THAT HAVE IMPACT ON TESTOSTERONE OR PROSTATE-SPECIFIC ANTIGEN LEVEL

The following lists of medications that are likely to affect analysis of efficacy are identified and will be finalized prior to the database lock. Any changes in this appendix after the finalization of the SAP will not be considered as changes in the planned analysis.

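### Sensitivity Analysis 2 drops whole patients for product use at any time on treatment, so escapes seen before first use are deleted; censoring at first use would keep them

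*SAP*

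**What the plan says.** SAP section 7.3.2 introduces four sensitivity analyses with a stated aim: "To assess the robustness of the primary analyses for Evaluation Criteria 1 and 2". The second keeps the censoring rules of section 7.3.1.2 and adds that "patients who had received concomitant medications and herbal supplements that could possibly affect testosterone level during study treatment will be excluded from the analysis".

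Four other places bear on how that sentence works:

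- Section 7.3.1.2 defines the event as "any testosterone test result rising above the castration level" from Week 5 Day 1 through Week 49 Day 1.
- For men who start a therapy known to suppress testosterone (Appendix Table 1), the same section says they "will be censored at the time of last testosterone assessment prior to the initiation of such therapies". Whichever of event or censoring comes first counts, so an earlier escape stays in.
- Section 5.6: "Medications are considered concomitant if medications were used during the study treatment period". Any use in that period qualifies, before or after an escape.
- Appendix 1: "The following lists of medications that are likely to affect analysis of efficacy are identified and will be finalized prior to the database lock". Its two tables cover therapies known to suppress testosterone and treatments that affect PSA. Neither lists products that only might affect testosterone.

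**The concern.** Membership of the analysis set depends on something that happens after first dose, and possibly after the outcome. Whole-patient exclusion has two consequences here. An escape already observed can vanish because of a later product. Valid castrate follow-up before the product is also thrown away. Men who stay longer on treatment have more time to become excludable, so exclusion can be tied to outcome even when the product has no effect.

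What is at stake is how this one check reads. For Criterion 1 it estimates a single-arm rate against a 90% threshold. For Criterion 2 it compares randomised groups after a selection made on post-baseline behaviour. If use is related to outcome, a difference from the primary result may reflect the deletion rule rather than any influence of the products.

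**Working it through.** **1. The plan's own base figures.** Section 2.2 assumes that "True probabilities of sustained testosterone suppression are 94% and 96% for relugolix and leuprolide acetate, respectively". It states about 90% power for Criterion 1 with 610 men and at least 99% for Criterion 2. Both reproduce and neither is disputed.

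- Criterion 1, exact binomial, n = 610 × 0.85 = 518: at least 480 successes are needed (one-sided error 0.022 at 90%), with power 91.2% at 94%.
- Criterion 1, log-log scale, n = 610: SE = √[0.06/(610 × 0.94)]/|ln 0.94| = 0.165. Then ln(−ln 0.90) − ln(−ln 0.94) = 0.532, and Φ(0.532/0.165 − 1.96) = 89.6%.
- Criterion 2, unpooled normal approximation: 99.97% at 610/305 and 99.88% at 518/259.

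**2. Two men under the two rules.** The product is one that might affect testosterone and is not in Appendix Table 1.

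| Man | Primary analysis | Sensitivity Analysis 2 as written | Censoring at first use |
|---|---|---|---|
| Escapes Day 57, product from Day 85 | event, Day 57 | absent | event, Day 57 |
| Castrate throughout, product from Day 300 | no event, followed to Day 337 | absent | castrate to Day 281 visit |

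**3. Size of the bias.** All usage figures are assumptions. Inputs:

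- True rate 94.0%, so 6% escape: half at Day 29, the rest spread evenly over the 11 visits from Day 57 to Day 337. No other censoring.
- A share u of men without escape uses a product by Day 337, at constant hazard λ = −ln(1 − u)/337.

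Let q_N = 1 − u be the chance that a man without escape is never flagged, and q_E the same chance for a man who escapes. Exclusion then reports

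0.94 q_N / (0.94 q_N + 0.06 q_E).

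With t the escape day, averaged over escape days:

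- Use unrelated to outcome: q_E = q_N.
- Threefold hazard after escape only: q_E = mean of exp[−λt − 3λ(337 − t)] = 0.888, 0.784, 0.601 for u = 5%, 10%, 20%.
- Use recorded only up to escape: q_E = mean of exp(−λt) = 0.983, 0.966, 0.930.
- Threefold hazard from Day 1: q_E = (1 − u)³ = 0.857, 0.729, 0.512.

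Example, second case with u = 5%: 0.94 × 0.95 = 0.8930; 0.06 × 0.888 = 0.0533; 0.8930/0.9463 = 94.4%.

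| Scenario | Exclusion: 5% / 10% / 20% use | Censoring at first use |
|---|---|---|
| Unrelated to outcome | 94.0 / 94.0 / 94.0 | 94.0 / 94.0 / 94.0 |
| Threefold after escape | 94.4 / 94.7 / 95.4 | 94.0 / 94.0 / 94.0 |
| Recorded only to escape | 93.8 / 93.6 / 93.1 | 94.0 / 94.0 / 94.0 |
| Threefold from Day 1 | 94.6 / 95.1 / 96.1 | 94.2 / 94.4 / 94.8 |

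The censoring column is the Kaplan-Meier product Π(1 − d/n) over the 12 visits, with first users leaving the risk set. If the use percentage is taken over all men rather than over those without escape, the threefold-after-escape row falls by less than 0.1 point (94.3% at 5% use).

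**4. Could a conclusion change?** Using the log-log interval without censoring:

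- At the planning rate, 37 events in 610 give 93.9% (91.7% to 95.6%), well clear of 90%.
- Near the threshold, 47 events in 610 give 92.3% with lower bound 89.9% (not met). Removing 5 men with escape and 28 without leaves 42 in 577: 92.7% with lower bound 90.3% (met). This case was chosen to show that a flip is possible. It is not a prediction.
- For Criterion 2, 37/610 against 12/305 gives −2.1 points, lower bound −5.0. Removing 11 escapes from relugolix, none from leuprolide, and about 5% of other men in each arm (29 and 15) gives 26/570 against 12/290: −0.4 points, lower bound −3.3. Both are far from −10.

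**The case against.** **This is only a supportive analysis.** That stands. Trial success rests on section 7.3.1, which does not use this exclusion. It is one of four checks, and Sensitivity Analysis 3 is deliberately conservative. A reader might infer that the rule compromises the trial's randomised comparison or its primary result. The SAP does not support that, because any selection is confined to section 7.3.2.2.

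**The drugs most likely to be started because of an escape are handled separately.** This largely stands. The sentence adds to the rules of section 7.3.1.2, so Appendix Table 1 therapies can be read as still censored with earlier escapes kept. What remains is products with a possible effect, such as herbal supplements. Nothing in the SAP shows that men who escape take these more often, so a reader should not assume an upward bias. If use is unrelated to outcome, there is none.

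**Use after an escape may be rare.** Section 7.3.1.2 implies that some men stop because of a non-castrate value, and on relugolix anything taken after the last dose falls outside the treatment period. This lowers the number affected but not equally by arm, since section 4.3.3 says: "For patients in the leuprolide acetate treatment arm, treatment period ends 12 weeks after the last leuprolide acetate injection".

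**The lists are fixed before database lock, and the revision history links 7.3.2.2 to regulatory comments.** Fixing the list settles which products count, not when use must occur. The comments are not shown, so whether this wording was requested is unknown.

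**Conclusion.** The point holds as a modest weakness in one sensitivity analysis. The loss of escapes observed before first use follows from the absence of a timing condition; the SAP does not state it as an intention, but no other section prevents it.

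Under the assumed 5% to 20% use, the reported rate moves by about +0.4 to +1.4 points if excess use follows escape, and by about −0.2 to −0.9 points if use is recorded only up to escape. These sizes rest wholly on assumed usage, since the SAP supplies none. The primary estimate, alpha and testing order do not change.

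It would go too far to say that agreement or disagreement with the primary result can never be interpreted. If few men are excluded, the check remains readable. Criterion 1 is exposed only when its lower bound lies close to 90%, and Criterion 2 has ample room.

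**What to change.** In section 7.3.2.2, replace exclusion from the analysis with censoring at the last testosterone assessment before first use of the product. State that escapes before first use count as events, and that only men already using the product at first dose are excluded.

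The cost is one SAP sentence, using a rule already in section 7.3.1.2. Section 4.4.3 imputes partial start dates but not completely missing ones, so a short convention is needed for those men.

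The fix has a limit. Censoring assumes that starting a product carries no information about later escape, an assumption section 7.3.1.2 already makes for suppressing therapies. If use before escape predicts escape, some bias remains: about 94.2% to 94.8% under a threefold rate from Day 1, against about 94.6% to 96.1% with exclusion.
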